**Dosing Regimen:**

Procedure	Duration	Dose regimen	
Screening	Up to 30 days prior to Baseline	Continuation of previous treatment	
Treatment Phase	Weeks 1-4	Starting dose 40 IU/kg/dose 2x/week	
		Low Risk	Switch to 50 IU/kg/dose Q5D until Week 8
		Medium Risk	Switch to 50 IU/kg/dose Q5D until end of study
	Week 9	High Risk	Continue 40 IU/kg/dose 2x/week until end of study
Week 9			
Abbreviations: Q5D = every 5 days; Q7D = every 7 days.			
a As determined by the investigator.			
Note: If $\geq 2$ muscle or joint bleeds (without evident trauma) occur within any given 8 week period during the 6 month study, then participant will be assigned to next highest frequency regimen. Per protocol, the treating investigator reserves the right to change a participant's regimen at any time if the treating investigator determines the score-determined regimen is not well-suited for the participant.			

**Data Monitoring/Other Committee:** No

## 1.2 Schema for Dosing Regimen Assignment

**Figure 1–1: Dosing Regimen Schema**

Abbreviations: PK = pharmacokinetics; Q5D = every 5 days; Q7D = every 7 days; SHL = standard half-life; vWF = von Willebrand factor.

a Score exception: if  $\geq 2$  muscle or joint bleeds (without evident trauma) occur within any given 8-week period during the 6-month study, then the protocol recommends assigning the participant to the next highest frequency regimen. Per protocol, the treating investigator reserves the right to change a participant's regimen at any time if they perceive the risk score-determined regimen is not well-suited for the participant.

## 1.3 Schedule of Activities (SoA)

Procedure	Visit 1 (Screening)	Intervention Period Months						Notes
		Visit 2 a (Baseline)	Visit 3	Visit 4	Visit 5 a	Visit 6 a (EOS/Early Withdrawal) b	Visit 7 (Safety Follow-up)	
		Up to 30 days before Day 1	Day 1	Month 1 (±7 days)	Month 2 (±7 days)	Month 3 (±7 days)	Month 6 (+14 days)	7 to 14 days after last dose
Contact	Visit	Visit	Phone	Phone	Visit	Visit	Phone	
Informed consent/assent	X							
Inclusion and exclusion criteria	X	X						Recheck clinical status before first dose of study medication.
Demography	X							
Weight	X				X			
Physical examination including height, weight		X				X		
Joint status (defined by ISTH)		X				X		
Highly sensitive serum pregnancy test (WOCBP only)	X	X c			X	X		
Physical activity level (contact/no contact/sedentary)		X d			X	X		
History of hemophilia	X							
Previous hemophilia treatment	X							
Other past and current medical conditions and surgical history (includes substance usage)	X							Substances: drugs
Total risk score calculation		X						
PROs e		X			X f	X		
FVIII levels: pre-dose, 15-30 minutes post-infusion, and at a minimum of 4 hours post-infusion		X g			X g	X g		A 3- or 5-day wash-out period is required for those patients whose previous product was an SHL or EHL, respectively
WAPPS-Hemo analysis					X h	X g, h		FVIII levels to be used from Visit 2 (if felt to be accurate levels) and Visit 5 (72-hour post-infusion level). See footnote h

Procedure	Visit 1 (Screening)	Intervention Period Months						Notes
		Visit 2 a (Baseline)	Visit 3	Visit 4	Visit 5 a	Visit 6 a (EOS/Early Withdrawal) b	Visit 7 (Safety Follow-up)	
		Up to 30 days before Day 1	Day 1	Month 1 (±7 days)	Month 2 (±7 days)	Month 3 (±7 days)	Month 6 (+14 days)	7 to 14 days after last dose
Laboratory assessments (hematology: CBC)	X							
Immunogenicity (FVIII inhibitor)	X							If suspect inhibitor to follow local clinical guidance for inhibitor testing
History of previous FVIII inhibitor	X							Please refer to eligibility criteria ( Section 5.1 and 5.2 ) for participants with a history of inhibitors. Recovery and half-life data for the SHL product should be extracted from medical records when available.
von Willebrand factor antigen (if not available in medical records)	X i							Please review Section 8.3.4 when drawing blood for von Willebrand factor antigen.
FVIII trough levels with study intervention					X j	X		Visit 5 72-hour level will also serve as the first of 2 trough levels for those on a 2x/week regimen
AE/SAE review	X k	←-----→					X	
Concomitant medication review	←=====→						X	
Dispense study intervention		X			X			
Administration of study intervention l,m		←=====→						
Return used vials					X	X		
Training on use of eDiary		X						
eDiary (bleed and study intervention) review		←=====→						

Abbreviations: AE = adverse event; CBC = complete blood count; EHL = extended half-life; EOS = End of Study visit; EQ-5D-5L = EuroQoL 5 Dimensions questionnaire; FVIII = human coagulation factor VIII; Haem-A-QoL = Haemophilia Quality of Life Questionnaire; ISTH = International Society on Thrombosis and Haemostasis; PGI-C = Patient's Global Impression of Change questionnaire; PRO = Patient Reported Outcome; SAE = serious adverse event; SHL = standard half-life; TSQM = Treatment Satisfaction Questionnaire for Medication; WOCBP = women of childbearing potential; WPAI = Work Productivity and Activity Impairment questionnaire.

a Visit 2 (Baseline) should occur 72 hours after the prior prophylaxis infusion. Visit 5 should occur 72 hours after the last Jivi infusion. Visit 6 should occur on the following days of the assigned prophylaxis regimen (i.e. as close as possible to the next infusion): on Day 4 for those on the 2x/week regimen, on Day 5 for those on the Q5D regimen, and on Day 7 for those

on less frequent dosing regimens.

b In case of withdrawal of consent, these activities will occur at the time of the return of the unused vials.

c If > 14 days since last menstrual period or from screening (Visit 1).

d Refers to the participant's usual physical activity level, based on the last 12 months. Level of activity will be defined as Sedentary, Low, or Medium/High. If a significant change in activity level is expected in the next 6 months, the criteria for the physical activity variable should be based on that anticipated level.

e Haem-A-QoL or Haemo-QoL, EQ-5D-5L, WPAI, TSQM. At Visit 6 (Month 6), PGI-C will also be collected.

f EQ-5D-5L only.

g If the investigator feels the baseline peak FVIII level at 15-30 minutes or 4-8 hours post-infusion at Visit 2 does not seem to be appropriate for the dose infused, then, if possible, the levels should be repeated at Visit 5 and the results also uploaded to WAPPS-Hemo. For those patients who do not have appropriate FVIII levels at either Visit 2 or Visit 5, the levels should be repeated at Visit 6.

h WAPPS-Hemo data entry should include FVIII levels measured pre-dose, post-infusion, hour 4-8 at Baseline (Day 1) and Month 3 (Visit 5; 72 hours after the last Jivi infusion).

i von Willebrand factor levels should be recorded within 12 months of screening. Please refer to [Section 8.3.4](#) for timing of von Willebrand factor blood draw.

j At Month 3 (72 hours after the previous infusion for all subjects). Post-infusion FVIII levels will be measured for all participants and included in the WAPPS-Hemo analysis.

k Only (S)AEs which are related to protocol-required study procedures will be recorded from the signing of the consent form until the start of study intervention.

l The first Jivi dose will be administered at the clinic at Baseline (Day 1) and may be administered at the clinic at Month 3 (Visit 5) and Month 6 (EOS/Early withdrawal; as long as the infusion does not occur before blood sampling). All other doses will be self-administered at home.

m In case of any infusion-related AE at a site visit, vital signs will be collected.

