#### 4.1.1 Screening

Screening examinations will only be performed after the participant (and parent[s] or legal guardian) has signed the informed consent form (ICF) and assent form (if necessary).

Participants will be screened for eligibility for up to 30 days prior to the treatment period. During this period, the inclusion and exclusion criteria will be evaluated and all screening procedures will be performed, including the risk score calculation based on the variables presented in [Table 4-1](#). Participants will be assigned a patient identification (PID) code via the Interactive Voice/Web Response System (IxRS) at the screening visit for use by the site only. All screening evaluations must be completed and reviewed prior to treatment allocation. Results of all screening evaluations must be reviewed by the investigator or his/her designee prior to enrollment of each participant into the study to ensure that all inclusion and exclusion criteria are met. During the screening period, participants will continue treatment with their current FVIII treatment.

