##### **Types of Participants and Disease Characteristics**

2. Previously-treated patients ( $\geq 150$  EDs) with congenital hemophilia A.

3. Prophylaxis with any SHL FVIII product with a stable frequency for at least 6 consecutive months within the last 12 months prior to screening, before entering the study and documented in medical records.
  - Stable frequency is defined as a minimum of 18 weeks of treatment in a 6 (consecutive) calendar month period in the 12 months prior to screening.
  - Patients can be on any non-Jivi EHL between the 6 -month stable SHL prophylaxis period and start of study treatment.
4. Documented bleeding rate (ABR) while on stable frequency prophylaxis for at least 6 consecutive months within the last 12 months prior to screening.
5. No current evidence ( $\geq 0.6$  BU/mL) of FVIII inhibitors.
  - If a participant has had a positive inhibitor titer in the past ( $\geq 0.6$  BU/mL on 2 occasions) but has been tolerized for at least 1 year since the last positive titer with at least 1 negative inhibitor assay test during that period, they can be enrolled.
  - If a participant has had a positive inhibitor titer in the past ( $\geq 0.6$  BU/mL) but did not require tolerization and has had at least 1 negative inhibitor assay test during a minimum period of at least 1 year since the last positive titer, they can be enrolled.
6. If they are human immunodeficiency virus (HIV) positive, cluster of differentiation 4 (CD4)+ lymphocyte count should be  $> 200/\text{mm}^3$  within 1 year before entering the study and documented in medical records.
7. Participants who are willing to complete an electronic diary (eDiary).

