## 6.8 Concomitant Therapy

Any medication or vaccine (including over-the-counter or prescription medicines, vitamins, and/or herbal supplements) that the participant is receiving at the time of enrollment or receives during the study must be recorded along with:

- Reason for use
- Dates of administration including start and end dates
- Dosage information including dose and frequency.

The Medical Monitor (Study Medical Expert) should be contacted if there are any questions regarding concomitant or prior therapy.

Bleeds which occur during the screening period (screening visit until Visit 2) will be treated with the participant's previous FVIII product.

All medications and blood products required by the participant after the ICF (and assent form) is signed, including FVIII products other than study intervention, will be listed in the appropriate case report form (CRF). All concurrent prescription and nonprescription medications including over-the-counter and alternative preparations (including herbal remedies, vitamins, and health food supplements), antibiotics, and pain medications being administered starting at least 3 months prior to screening will be recorded in the CRF and throughout the treatment and safety follow-up periods.

All planned vaccinations should be completed at least 2 weeks prior to start of study intervention. If a vaccination (including the COVID-19 vaccine) is to occur during the study, the vaccination should occur no more than 2 days after a Jivi infusion to prevent any potential bleeding at the injection site.

The participant should not be taking any other investigational drug while receiving treatment with Jivi, and all SHL prophylactics will have been stopped at least 3 days prior to the start of Jivi administration. All bleeding events that occur in participants receiving prophylactic infusion after the start of treatment (Visit 2) will be treated with Jivi as outlined in the approved prescribing information. After treatment of bleeding, the prophylactic Jivi regimen will be resumed according to assigned dosing schedule.

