### 11.7.2 Visit 2 – Baseline (Day 1)

This visit will serve as the Baseline Visit; it will include the first administration of study intervention. The Baseline Visit should take place within 30 days after the screening visit.

This visit should start with the following assessments:

- Confirmation of eligibility including check of laboratory test results

Note: Participants must have negative results from the local laboratory for inhibitory antibodies against FVIII (< 0.6 BU/mL determined with the Bethesda assay as per local clinical practice)

Thereafter, the following procedures and assessments will be performed and data recorded:

- Physical examination including height and weight
- Collect information on physical activity level (medium/high [contact sports]; low [non-contact sports]; sedentary). Please see [Table 4–1](#) and [Figure 4–1](#).
- Assessment of joint status
- Concomitant medication review
- AE/SAE/AESI review
- Administration and completion of PRO questionnaires (Haemophilia Quality of Life [Haem-A-QoL or Haemo-QoL], EuroQoL 5 Dimensions [EQ-5D-5L], Treatment Satisfaction Questionnaire for Medication [TSQM], and Work Productivity and Activity Impairment [WPAI] questionnaires)
- Blood sample collection **before** administration of study intervention for incremental recovery of Jivi (FVIII levels)
- Infusion of Jivi at study site
- Procedures and sample collection **after** administration of study intervention for incremental recovery of Jivi (15 to 30 minutes after end of infusion and at a minimum of 4 hours after end of infusion to assess FVIII levels; see [Section 8.5.1](#))
  - In case of any infusion-related AE, vital signs will be collected.
- Pregnancy test for female participants if visit occurs >14 days after last menstrual period
- Bleeding risk score calculation and prophylaxis regimen selection
- Dispense study intervention for home infusions
- Instruction on the treatment regimen to be administered to the participant
- Check of eDiary entries and bleeding history

Begin regular monthly contact between participant and the site to check eDiary documentation and review AEs and concomitant medication use until the EOS/Early Withdrawal.

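### The Schedule of Activities times Visit 2 at 72 hours after the last infusion for everyone, but requires a 5-day wash-out after an EHL, a 48-hour inconsistency (minor)

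*Protocol*

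**What the plan says.** In Protocol 1.3 (Schedule of Activities), footnote a is attached to the Visit 2 column: "Visit 2 (Baseline) should occur 72 hours after the prior prophylaxis infusion". It gives no window and does not distinguish between products. The note on the FVIII-levels row, which is marked at Visit 2, reads: "A 3- or 5-day wash-out period is required for those patients whose previous product was an SHL or EHL, respectively".

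EHL users can reach Visit 2. Inclusion Criterion 3 states: "Patients can be on any non-Jivi EHL between the 6 -month stable SHL prophylaxis period and start of study treatment". Section 4.1.1 adds: "During the screening period, participants will continue treatment with their current FVIII treatment". So for a participant on an EHL, the infusion before Visit 2 is an EHL infusion.

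Two other places could have settled the interval:

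- Section 6.8 covers SHL only: "all SHL prophylactics will have been stopped at least 3 days prior to the start of Jivi administration".
- Section 11.7.2, the Visit 2 description, limits only the time since screening: "The Baseline Visit should take place within 30 days after the screening visit". It gives no interval after the last infusion.

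The levels drawn at Visit 2 are used for incremental recovery (section 8.5.1) and for WAPPS-Hemo. Footnote h says that "WAPPS-Hemo data entry should include FVIII levels measured pre-dose, post-infusion, hour 4-8 at Baseline (Day 1") and at Month 3. The row note on WAPPS-Hemo makes use of the Visit 2 values conditional: "FVIII levels to be used from Visit 2 (if felt to be accurate levels").

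**The concern.** The first Jivi infusion and the pre-dose sample both take place at Visit 2, so the wash-out has to be complete by then. For an EHL participant, a visit at 72 hours satisfies footnote a and falls short of the wash-out. A visit at 5 days satisfies the wash-out and departs from footnote a. The sponsor judged 5 days necessary after an EHL, yet the footnote that a coordinator would naturally schedule from still gives the SHL interval.

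What is at stake is narrow. Residual activity of the earlier EHL could be present in the Visit 2 pre-dose and post-infusion levels. Section 8.5.2 lets WAPPS-Hemo entry go ahead with or without a pre-infusion level. If the pre-dose value were left out, nothing in the entered data would show that residual.

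**Working it through.** **Step 1. Compare the two rules (Protocol 1.3).**

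| Previous product | Footnote a | Wash-out note | Difference |
|---|---|---|---|
| SHL | 72 h | 3 × 24 = 72 h | 0 h |
| EHL | 72 h | 5 × 24 = 120 h | 120 − 72 = 48 h |

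**Step 2. Size of the residual.** The documents give no half-life or peak for the earlier EHL, so these are assumptions shown as ranges.

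*Single dose, half-life h of 12 to 20 h, prior peak of 80 to 120 IU/dL.* Residual = peak × 2^(−t/h).

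- At 72 h: 80 × 2^(−72/12) = 80 × 0.015625 = 1.25, up to 120 × 2^(−72/20) = 120 × 0.08247 = 9.90 IU/dL.
- At 120 h: 80 × 2^(−120/12) = 0.08, up to 120 × 2^(−120/20) = 1.88 IU/dL.
- Carried from a 72-hour visit into the 4–8 h sample: 1.25 × 2^(−8/12) = 0.79, up to 9.90 × 2^(−4/20) = 8.62 IU/dL.

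*Wider case: steady state with dosing every 72 h, rise of 50 to 150 IU/dL, half-life of 12 to 24 h.* Residual = rise × 2^(−t/h) / (1 − 2^(−72/h)).

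- At 72 h: 50 × 0.015625 / 0.984375 = 0.79, up to 150 × 0.125 / 0.875 = 21.43 IU/dL.
- At 120 h: 50 × 0.000977 / 0.984375 = 0.05, up to 150 × 0.03125 / 0.875 = 5.36 IU/dL.

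**Step 3. Would the SAP's validity rule catch it?** SAP 4.1.1.5 rejects a pre-infusion level above 37.5% after 3 days. Taking 1 IU/dL as 1%, the largest value above is 21.43, so the rule would not flag a short wash-out. It is a plausibility limit and was not written to check wash-out.

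**Step 4. Incremental recovery.** The SAP formula subtracts the pre-infusion level, so the only error is the decay of the residual over about 0.5 h, which is residual × (1 − 2^(−0.5/h)).

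- Low end: 1.25 × (1 − 2^(−0.5/12)) = 0.036 IU/dL.
- Top of the single-dose range: 9.90 × (1 − 2^(−0.5/20)) = 0.17 IU/dL.
- Top of the wider range: 21.43 × (1 − 2^(−0.5/24)) = 0.31 IU/dL.

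Against an assumed rise of 80 IU/dL these are about 0.04%, 0.21% and 0.38%, which is negligible.

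**Step 5. What does not use these levels.** Favorable outcome is built from ABR, prescribed infusion frequency and regimen changes, and the risk score from five variables that do not include an FVIII level. The secondary endpoints are bleeds, frequency, questionnaires and target joints. The Visit 5 and Visit 6 troughs are taken months later, on Jivi.

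**Step 6. What discarding would cost.** Section 8.5.2 asks for at least 3 post-infusion time points. Visit 2 supplies two (15–30 minutes and 4–8 hours) and the Visit 5 72-hour level supplies the third. Dropping the Visit 2 values leaves 3 − 2 = 1 unless levels are repeated.

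**The case against.** The strongest reply is that the two statements do not have equal force. Footnote a is advisory, while the wash-out note is mandatory and names each product. Specific, mandatory text normally governs general, advisory text, so a site that reads the whole table would wait 5 days and depart only from a recommendation. That largely stands. A reader might infer that the schedule is unworkable for EHL participants, and the documents do not support that. What remains is that no order of precedence is stated and the scheduling footnote gives the wrong interval for this group.

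There are also safeguards:

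- Footnote h asks for the pre-dose level to be entered.
- Visit 2 values are used only if judged accurate.
- Footnote g provides repeats at Visit 5 or 6 when a Visit 2 post-infusion level looks wrong for the dose.
- Section 8.5.2 describes expert cleaning, manual validation and an outlier search.
- A short interval can be found from the listed sampling times (SAP 4.4.3), the days since the previous treatment ended (SAP 4.6.2), deviation reporting (SAP 4.6.1) and the validity review (SAP 3).

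These reduce the exposure, but a residual of a few IU/dL might not look inappropriate to anyone.

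A reader might also infer that the WAPPS-Hemo estimates would be biased. The documents do not show that. The pre-dose level is meant to be entered, and how the service handles it is not described. The ranges above size a residual and not an effect on any reported parameter.

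Finally, the reach of a new amendment may be small. Amendment 3, which opened entry to EHL users, expected 20–25 participants by the end of 2023, and SAP version 3 is dated 09 JAN 2024. Actual enrollment dates are not shown.

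**Conclusion.** This is a minor internal inconsistency. For participants entering on a non-Jivi EHL, footnote a gives an interval 48 h shorter than the wash-out that the same table requires, and neither section 6.8 nor section 11.7.2 settles the matter. The wash-out note probably prevails, but that is an inference. The 5-day choice itself is not in question.

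The 48 h follows directly from the text. The residual, about 1.2 to 9.9 IU/dL at 72 h against 0.1 to 1.9 at 120 h (0.8 to 21.4 against 0.05 to 5.4 under the wider assumptions), depends on assumed half-lives and peaks. Only exploratory Visit 2 FVIII levels and WAPPS-Hemo inputs are exposed, and incremental recovery is essentially unchanged. The documents do not say how many participants entered on an EHL, so the number affected may be zero.

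**What to change.** Change footnote a so that Visit 2 falls *72 hours after an SHL infusion or 5 days (120 hours) after an EHL infusion*. Add the 5-day EHL stop to section 6.8 and repeat the interval in section 11.7.2 for consistency. The gap between visit timing and wash-out is then 0 h for both products.

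For any EHL participant already sampled before 5 days:

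- record the deviation;
- confirm that the pre-dose level was entered in WAPPS-Hemo;
- where possible, use the footnote g repeat at Visit 5 or 6.

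Do not discard the Visit 2 levels automatically. That could leave too few post-infusion points for an estimate. A flag raised only at final data review would also come after the site has run WAPPS-Hemo at the end of Visit 5.

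The cost is a wording change in three places, with IRB approval under section 11.1.1; if a further amendment is made for other reasons, it can be included there. Section 2.1 gives EHL dosing intervals of 3 to 5 days, so a 5-day wash-out adds 5 − 5 = 0 to 5 − 3 = 2 days to the usual interval, which the existing note already requires. The check on participants already sampled uses data already collected and needs no extra tables; only a repeat would add sampling, which footnote g already provides for.

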## 2. Introduction

### 2.1 Study Rationale

Hemophilia A is an X-linked, inherited, genetic bleeding disorder characterized by deficiency of human coagulation factor VIII (FVIII) ([Srivastava et al., 2013](#); [NHF, 2021](#)). Hemophilia A patients are treated by intravenous (IV) administration of FVIII on-demand or as a prophylactic therapy administered 2 to 4 times a week with FVIII products. The need for frequent IV infusion creates barriers to patient compliance and makes adherence to prophylaxis difficult. According to the World Federation of Hemophilia (WFH), it is estimated that only between 25% and 30% of hemophilia patients globally are adequately diagnosed and managed ([WFH, 2021](#)).

Prophylactic regimens lead to favorable outcomes by reducing the amount of spontaneous bleeds. The hemophilia A treatment landscape is evolving from using standard half-life (SHL) recombinant coagulation FVIII (rFVIII) products for routine prophylaxis to extended half-life (EHL) products. Switching patients from a SHL to an EHL factor product allows for the maintenance of efficacy with less frequent dosing, leading to significant benefit in long-term outcomes and quality of life (QoL) improvement for patients with hemophilia.

The EHL products, which provide treatment options with dosing intervals of 3 to 5 days for prophylactic treatment (such as Esperoct®, Eloctate®, Adynovate®, Jivi), have been approved recently in several countries worldwide. Any other FVIII products are considered SHL. Jivi was developed as an EHL FVIII for prophylaxis, peri-operative management, and treatment of acute bleeding events. Site-specific PEGylation was used to increase the FVIII half-life, resulting in a longer duration of the effect by raising plasma levels for a longer duration, thereby allowing for less frequent dosing when used in a prophylaxis setting. Efficacy and safety of Jivi were demonstrated in the pivotal trials ([Reding et al., 2017](#); [Coyle et al., 2014](#)).

There is still no agreement on what constitutes an optimal prophylactic treatment regimen in adults with hemophilia. Consequently, the dose and frequency of infusions are often determined according to local established practice and left to clinicians' judgment. In general, the current strategies used for prophylaxis can be divided into those that aim to maintain FVIII activity  $> 1$  IU/dL and those that are guided by the clinical bleeding patterns of individual patients. Currently, if Health Care Professionals (HCPs) do not rely on traditional pharmacokinetic (PK) or population PK analysis of rFVIII decay curves to determine an optimal treatment regimen when patients are switching to EHL products, the most common approach is to rely on assumptions that are informed by patients' characteristics and clinical history. This "trial and error" approach could lead to suboptimal protection of the patient and cause harmful, potentially avoidable bleeds or, on the other hand, an excessive use of rFVIII products that will have an economic impact and might not ease the burden of frequent infusions ([Yu et al., 2019](#)). The difficulty in determining the most optimal prophylaxis regimen for a patient lies with the disease variability among patients; it is comprised of a series of phenotypic and biologic parameters that render every patient unique in his/her treatment needs and begs for an individualized tailored approach.

The challenge, then, is to optimize hemophilia therapy by individualizing prophylactic regimens to the needs of each patient, while reducing the burdens associated with IV infusion. Thus, the clinical community has several unanswered questions regarding the most appropriate treatment regimen for a patient switching products and the best approach to

achieve an optimal therapeutic and economic regimen with the first attempt. Clinicians rely on their own clinical judgment, using criteria that potentially have an impact on predicting the right dosing regimen. However, these criteria have neither been studied prospectively to select the optimal treatment regimen nor were they studied for their combinatorial usefulness.

In this proposed clinical study, the effect of using a new risk score approach, based on the best known predictive phenotypic and biologic variables, to select the most appropriate prophylaxis regimen for reaching a favorable outcome will be assessed for participants switching from SHL to Jivi. The scoring approach in this study has not yet been validated and is different from classical risk-based models in that the score allocation and the dosing regimen itself has an influence on the outcome of interest. Due to the nature of the study, the inclusion of sub-populations such as mild/moderate hemophilia patients, women, and patients with past FVIII inhibitors should not prevent them from participating.

The scoring approach will be composed of 5 individually weighted variables: pre-study bleeding phenotype, previous treatment frequency, number of active target joints, von Willebrand factor (vWF) antigen levels, and physical activity. These variables were selected on the basis of the existing data regarding their established or potential role in determining the most appropriate EHL regimen.

The relevance of pre-study bleeding patterns and prior treatment frequency in tailoring an appropriate prophylaxis regimen is supported by the results of the Jivi PROTECT VIII study. In the main study, significant improvements in ABR were demonstrated for patients in 3 prophylaxis regimens selected on the basis of prior bleeding pattern ([Reding et al., 2017](#)). Importantly, ABR and total bleeds were further reduced after on-study dosing adjustments (e.g. changes from Q7D to Q5D dosing) were made based on treatment response and individual patient preference ([Lalezari et al., 2019](#)). Clinical outcomes have also been correlated with baseline disease burden as measured by the presence or absence of target joints. Substantially lower health-related QoL scores were observed in hemophilia patients with 2 or more target joints affected, and score decreases were likewise recorded in patients with only one active joint ([Carroll et al., 2019](#)). Variability at the cellular level should also be accounted for when assessing the value of different prophylaxis regimens. The pharmacokinetics of FVIII is regulated by the clearance of vWF from plasma ([Swystun et al., 2019](#)). Therefore, individual differences in vWF levels and the genetic determinants that impact FVIII-vWF binding will influence the response to EHL FVIII prophylaxis regimens. The final variable in the scoring approach weighs the link between physical activity and bleed risk. Data regarding the bleeding risk associated with various levels of physical activity is inconclusive due to variations in frequency, intensity, and the age of the patient. However, risk has been associated with high levels of physical activity and, in one study, this risk was mitigated by typical prophylactic regimens ([Broderick et al., 2012](#)). Dose and frequency modifications in alignment with the activity level of the patient may improve clinical response.

Each of the variables will have an assigned maximum and minimum value for a given participant that are summed into a personalized risk score for each participant. With defined value thresholds, this total risk score is expected to predict the most appropriate Jivi regimen (2x/week, Q5D, or less frequent dosing [e.g. Q7D]) leading to a favorable outcome for at least 70% of the participants enrolled in this study.

A favorable outcome is defined as:

- no change of the risk score-assigned dosing regimen during the study, with one of the following:

- improved ABR versus pre-study ABR and decreased frequency of administration versus pre-study frequency.
- improved ABR versus pre-study ABR with similar frequency of administration vs. pre-study frequency.
- decreased frequency of administration versus pre-study frequency and similar ABR versus pre-study ABR.

Pre-study ABR and treatment frequency is based on data from a minimum of 6 continuous months (up to a maximum of 12 months) of stable SHL prophylaxis at any given time within the 12 months prior to the screening visit. Stable SHL prophylaxis is defined as a minimum of 18 weeks of treatment in a 6 (consecutive) calendar month period in the 12 months prior to the screening visit. Pre-study ABR will be determined by treatment infusion history or by a participant's bleed diary, if one is available. This cannot be controlled or mitigated in the study design (refer to [Section 6.3](#) for additional details).

